2.1.2. Endpoints

Primary Endpoint

The primary endpoint is the hospital recovery scale as assessed on Day 6.

Secondary Endpoints

The secondary endpoints are:

- Safety and tolerability based on assessment of AEs, clinical laboratory assessments, 12-lead electrocardiograms (ECGs), vital signs, and peripheral capillary oxygen saturation.
- Time from start of study drug to hospital discharge and total length of hospital stay.
- Time from ICU admission to ICU discharge and total time in ICU. Time in ICU before start of study drug is discarded.
- Time from start to end of mechanical ventilation and total time on mechanical ventilation. Time on mechanical ventilation before start of study drug is discarded.
- The hospital recovery scale as assessed each separated day from Days 2 to 14 (excluding the primary time point).
- Time to return to daily activities.
- Incidence of complications associated with influenza after the start of study treatment:

- Pulmonary complications:

The pulmonary complications of influenza include respiratory failure, primary viral pneumonia, secondary bacterial pneumonia (including pneumonia attributable to unusual pathogens), exacerbations of chronic underlying pulmonary diseases such as COPD, asthma, and bronchitis.

- Respiratory failure: defined as either hypoxemic respiratory failure characterized by an arterial oxygen tension (PaO_2) lower than 60 mmHg with a normal or low arterial carbon dioxide tension (PaCO_2), or hypercapnic respiratory failure characterized by a PaCO_2 higher than 50 mmHg.
- Primary viral pneumonia: a progressive event involving the lower respiratory tract with bilateral and/or diffuse radiological findings. No bacterial agent is identified using sputum cultures.
- Secondary bacterial pneumonia (including pneumonia attributable to unusual pathogens): a clinical event compatible with lower respiratory tract involvement, with lobar infiltrates on radiological studies and/or microbiological isolate of a bacterial pathogen, including unusual pathogens.
- Exacerbations of chronic underlying pulmonary diseases such as COPD and asthma: subjects with documented medical history of COPD or asthma with a sudden worsening of symptoms and deteriorating respiratory function (the latter as evidenced by worsening hypoxia, tachypnea, etc.) The event must start before a full recovery from the influenza infection occurred.
- Bronchitis
- Extrapulmonary complications:
 - Cardiovascular and cerebrovascular disease (eg, myocardial infarction, congestive heart failure, arrhythmia, stroke)
 - Muscular disorders (eg, myositis, rhabdomyolysis)

-
- Central nervous system [CNS] involvement
 - Acute exacerbation of chronic kidney disease
 - Decompensation of previously controlled diabetes mellitus
 - Other infections (eg, sinusitis, otitis)
 - All-cause mortality.
 - Incidence and duration of antibiotic treatment.
 - The number (proportion) of subjects needing extended treatment.
 - The number (proportion) of subjects requiring re-hospitalization.
 - The number (proportion) of subjects not hospitalized at Day 6.
 - Time to clinical response. Clinical response is defined as achieving 4 of the 5 following vital sign resolution criteria, including at least the fever and oxygen saturation criteria, maintained for at least 24 hours:
 - having no fever (without the use of antipyretics within 8 hours),
 - oxygen saturation of at least 94% without oxygen supplementation or return to pre-influenza infection oxygen saturation (in patients with a known pre-influenza oxygen saturation level <94%),
 - improved respiratory status (a respiratory rate ≤ 24 breaths per min without supplemental oxygen or return to pre-influenza infection supplemental oxygen requirement in patients with chronic oxygen use),
 - heart rate 100 beats per minute or lower,
 - systolic blood pressure of 90 mmHg or higher without inotropic support given within 2 hours of assessment.
 - Time to respiratory response. Respiratory response is defined as achieving the following 2 criteria for at least 24 hours:
 - improved oxygen saturation of at least 94% without oxygen supplementation (return to pre-influenza infection oxygen saturation in patients with a known pre-influenza oxygen saturation level <94%) and
 - improved respiratory status characterized by a respiratory rate ≤ 24 breaths per min without supplemental oxygen or return to pre-influenza infection supplemental oxygen requirement in patients with chronic oxygen use.
 - PK parameters of pimodivir (ie, plasma concentration just prior to the beginning or at the end of a dosing interval [C_{trough}], C_{max} , t_{max} , and AUC_{12h}), as determined by population PK analysis.
 - Time to viral negativity by qRT-PCR and viral culture.
 - Viral load over time by qRT-PCR and viral culture.
 - The emergence of viral resistance against pimodivir detected by genotyping and/or phenotyping.
-

- The acceptability of the pimodivir formulation in adolescents, as measured by a taste and swallowability questionnaire.

Exploratory Endpoint

- A patient-reported outcome (PRO) based on subjects' ratings on the influenza symptom diary will be formulated.

Refer to Section 9, Study Evaluations, for evaluations related to endpoints.

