Blood oxygen saturation will be measured using a standard pulse oximeter. If possible, the same type of probe should be used for all subjects enrolled at the site while they are hospitalized. The SpO₂ should be measured either in a sitting or supine position after 5 minutes of rest in a quiet environment. Subjects should be encouraged to sit still during the measurements. Pulse oximetry measurements using finger, toe, earlobe or frontal sensors are considered acceptable. If using the digits, nail polish should be removed, and warmth and capillary refill should be assessed, since adequate arterial pulse strength is necessary for obtaining accurate SpO₂ measurements. The sensor should not be placed on sites distal to indwelling arterial catheters, blood pressure cuffs, or venous engorgement (eg, arteriovenous fistulas, blood transfusions). If supplemental oxygen is provided to the subject by either nasal cannula, face mask, or a reservoir system, remove supplemental oxygen while the subject is appropriately monitored. Wait for either 5 minutes to elapse with oxygen saturation maintained at or above 94%, or until saturation declines to less than 94%. (For subjects with known pre-influenza illness SpO₂ levels of <94%, the pre-influenza SpO₂ level should be used as target level instead of 94%). Document those findings, then either return to previous level of supplemental oxygen therapy or discontinue therapy. For subjects receiving invasive or non-invasive mechanical ventilation, peripheral oxygen saturation should be measured with the ventilatory support in place, and it should be recorded that the measurement was with supplemental oxygen.

Blood pressure, pulse rate, and respiratory rate measurements should be preceded by at least 5 minutes of rest in the supine position in a quiet setting without distractions (eg, television, cell phones). These measurements will be assessed with a completely automated device. Manual techniques will be used only if an automated device is not available.

The level of consciousness will be measured according to the ACVPU scale (alert, new confusion, voice, pain, unresponsive).¹⁰

- Alert: The subject is fully awake. This subject will have spontaneously opening of the eyes, will respond to voice, and will have motor function.

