	
Within 1 timepoint the assessments of the different parameters are taken together for evaluating the clinical response and the time of the last record within that time point is used. Unscheduled assessments are not taken into account. When multiple assessments for 1 parameter occur within one timepoint then only the last is used for that parameter.
 
Table 4: Resolution Criteria for Vital Signs
 
  
 Assessment	Resolution Criterion	
   
 Temperature	Oral temperature ≤ 37.0 °C (without the use of antipyretics within 8 hours)*¹	
 
 Oxygen saturation	a) $\geq 94\%$ on room air without supplemental oxygen*² b) In case pre-influenza infection oxygen saturation $< 94\%$*³: Return to pre-influenza oxygen saturation*⁴	
 
 Respiration rate	≤ 24/min or return to pre-influenza infection oxygen requirement in patients with chronic oxygen use*^{4,5}	
 
 Heart rate	≤ 100/min	
 
 Systolic blood pressure	≥ 90 mmHg (without inotropic support given within 2 hours of assessment) *⁶	
  
 
*¹Based on the Vital Signs form, question “Were there any antipyretic medications given within 8 hours before temperature measurement?”
 
*²Based on the oxygen saturation level measured on room air and “YES” on the question ‘Is the patient able to sustain a blood oxygen saturation $\geq 94\%$ when breathing room air for 15 min at any time on the day of assessment?’ on the vital signs form.
 
*³ If pre-influenza oxygen saturation level is below 94% and measured on room air
 
*⁴Return to pre-influenza infection oxygen requirement is based on the oxygen supplementation form: “Has supplemental oxygen administration returned to that level provided prior to the current respiratory infection?”
 
*⁵Chronic oxygen use is based on the question “Does the subject require chronic oxygen”
 
*⁶ Inotropic support given within 2 hours of assessment as recorded in the vital signs form.
	Assessment	Resolution Criterion	Temperature	Oral temperature ≤ 37.0 °C (without the use of antipyretics within 8 hours)* ¹	Oxygen saturation	a) $\geq 94\%$ on room air without supplemental oxygen* ² b) In case pre-influenza infection oxygen saturation $< 94\%$ * ³ : Return to pre-influenza oxygen saturation* ⁴	Respiration rate	≤ 24 /min or return to pre-influenza infection oxygen requirement in patients with chronic oxygen use* ^{4,5}	Heart rate	≤ 100 /min	Systolic blood pressure	≥ 90 mmHg (without inotropic support given within 2 hours of assessment) * ⁶

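### SAP Table 4 does not implement the protocol's saturation and respiration criteria for clinical and respiratory response, chiefly in subjects whose usual SpO2 is below 94%

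*Protocol*

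**What the plan says.** **Protocol 2.1.2 (repeated in 11.4).** The saturation criterion is "oxygen saturation of at least 94% without oxygen supplementation or return to pre-influenza infection oxygen saturation", the return route applying "in patients with a known pre-influenza oxygen saturation level <94"%. Nothing is said about whether that usual value was measured on air or on oxygen. The respiration criterion is a rate of at most "24 breaths per min without supplemental oxygen or return to pre-influenza infection supplemental oxygen requirement in patients with chronic oxygen use". Saturation is mandatory for clinical response, and the two criteria together define respiratory response. On measurement, Protocol 9.6.4 says that for subjects with a low usual value the pre-influenza "level should be used as target level instead of 94"%.

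**SAP 5.3.1.1, Table 4.** Route (a) of the saturation row is at least 94% on room air. Route (b), for low usual values, is worded "Return to pre-influenza oxygen saturation" and carries two footnotes. Footnote 3 sets who may use it: "If pre-influenza oxygen saturation level is below 94% and measured on room air". Footnote 4 sets how the return is read, from an item on the oxygen supplementation form: "Has supplemental oxygen administration returned to that level provided prior to the current respiratory infection". The respiration row is 24/min or less, or return to the usual oxygen requirement in chronic users (footnotes 4 and 5). It does not require that no oxygen is being given.

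The SAP Introduction says that it is to be read together with the protocol. It declares no departure on these two endpoints.

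**The concern.** Table 4 is what will be programmed, and it differs from the protocol in three places.

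1. The return to usual saturation is decided by oxygen prescribing, not by saturation.
2. The return route is closed to subjects whose low usual value was recorded on oxygen.
3. The respiration row loses its no-oxygen condition.

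Subjects with a low usual SpO2 are enrolled by design: Protocol 4.1, inclusion criterion 5, gives them their own SpO2 rule. For these subjects the date of response could reflect when oxygen was reduced, or response might not be reached at all. The endpoints reported would then not be the ones the protocol defines.

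**Working it through.** The plan gives no figure to reproduce here. The check sets the two rules side by side and applies them to the same states.

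**Rules, read literally, at one timepoint**

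- Protocol saturation: (SpO2 ≥94% and no oxygen) or (usual <94% and SpO2 at or above usual).
- Protocol respiration: (rate ≤24 and no oxygen) or (chronic user and oxygen back at the usual level).
- SAP saturation: (SpO2 ≥94% on room air, no oxygen) or (usual <94% *on room air* and form item = yes).
- SAP respiration: (rate ≤24) or (chronic user and form item = yes).
- Respiratory response needs both criteria.

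**Three illustrative subjects**

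- *Usual 92% on room air, now off oxygen at 87%, rate ≤24, form item yes.* Protocol: 87 < 92, not met. SAP: met.
- *Chronic oxygen user, usual value <94% on room air, form item yes.* In the SAP the same answer satisfies both rows, so respiratory response reduces to one yes/no item.
- *Chronic oxygen user, usual 91% recorded on oxygen, now 91% at the usual oxygen level.* Protocol: both criteria met. SAP: footnote 3 closes route (b), and ≥94% on room air is required.

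**Enumeration**

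The states combine chronic oxygen use, current SpO2 (≥94% on air, at usual, below usual), current oxygen (none, usual level, above) and rate ≤24 or not. 'Usual level' applies to chronic users only, and 'at usual' is not a separate level when usual is ≥94%. Subjects with a usual value recorded on oxygen are taken to be chronic users. The counts are:

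- usual ≥94%: 2×3×2 + 2×2×2 = 20
- usual <94% on air: 3×3×2 + 3×2×2 = 30
- usual <94% on oxygen: 3×3×2 = 18

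The documents do not say how the form item is coded when no oxygen is given, so both codings were run. Cells show the states credited with respiratory response.

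| Usual SpO2 | States | Protocol | SAP, item 'yes' if no oxygen | SAP, item missing if no oxygen |
|---|---|---|---|---|
| ≥94% | 20 | 3 | 3 | 2 (1 missed) |
| <94%, room air | 30 | 10 | 10 + 5 = 15 (5 wrongly credited) | 10 + 2 − 4 = 8 (2 wrongly credited, 4 missed) |
| <94%, on oxygen | 18 | 8 | 8 − 6 = 2 (6 missed) | 8 − 7 = 1 (7 missed) |

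Every wrongly credited state has SpO2 still below usual, with oxygen at or below its usual level. In the last row, the one or two states that the SAP still credits all need ≥94% on room air with no oxygen. These are counts of logical states, not of patients, and cannot be read as proportions.

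**Respiration row**

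With route (a) taken strictly as no oxygen, the omitted condition changed no state on its own. It matters when SpO2 is read after oxygen is briefly removed and may then be resumed, as Protocol 9.6.4 describes, while the rate is counted on oxygen. Footnote 2 decides route (a) from a room-air reading and a sustained-saturation question, not from oxygen start and stop times. A subject still on oxygen could therefore pass both SAP rows. This can happen at any usual SpO2.

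**The case against.** **Footnote marker.** Footnote 4's own text refers to the oxygen requirement, which is the wording of the respiration row. Its marker on the saturation row may be a slip, and the SAP is to be read with the protocol. That is plausible. But the SAP gives no other rule for return to saturation, so the row needs correcting either way.

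**Room-air condition.** It is not arbitrary. The hospital recovery scale and the extension criteria compare room-air SpO2 with the usual value, and Attachment 6 uses a room-air pre-influenza record. Protocol 9.6.4 takes readings off oxygen except in ventilated subjects, and a room-air reading cannot fairly be compared with a usual value recorded on oxygen. This stands, and it rules out simply deleting the condition.

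**Stronger readings that a reader might infer**

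- *Response is impossible for subjects with a usual value on oxygen.* Route (a) stays formally open, so it is only practically unattainable.
- *A subject never given oxygen cannot respond.* That depends on form coding which the documents do not show.
- *The endpoints lose substantial power.* Simulations (600 subjects, Gehan test, three assessments daily for 14 days, 1500 replicates) gave 88–89% power, falling to 82–83%, 74–77% and 58–59% if 5%, 10% or 20% of subjects never respond. These are upper-end illustrations. The shares, the hazard ratio of 1.35 and the 5-day control mean are assumptions, and the whole low-SpO2 group is made non-responding. At 1–2% never responding, power was 87%, unchanged within simulation error. The plan claims no power for these endpoints.

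**Conclusion.** The mismatch is real and worth correcting. Followed literally, Table 4 can code a subject as resolved with SpO2 still below the usual value. It also leaves subjects whose low usual value was recorded on oxygen with a target that they will in practice not meet. The omitted no-oxygen condition in the respiration row is a lesser mismatch and is not specific to the low-SpO2 group.

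The reach is limited to two secondary endpoints. Both are outside the seven-endpoint confirmatory sequence (SAP 5.1.1), and their objectives are worded as investigation, not superiority. The rule applies alike to both blinded arms. The effect on the estimates cannot be computed, because the documents give neither the share of subjects with usual SpO2 below 94% nor how many of those values were recorded on oxygen. The conclusion rests on the literal text of Table 4 and its footnotes.

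**What to change.** Amend SAP Table 4 before unblinding.

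1. **Saturation, route (b).** Compare SpO2 at the timepoint with the recorded pre-influenza SpO2, and remove footnote 4 from this row. Attachment 6 already uses that record. Only the record should be taken over, not the three-point margin of the recovery scale, because the protocol asks for return to the usual value.
2. **Footnote 3.** Reconcile it with Protocol 2.1.2 by requiring matching oxygen conditions: a room-air usual value against a room-air reading, and a usual value recorded on oxygen against a reading on the usual oxygen level. State how a timepoint is coded when no matching reading exists.
3. **Respiration rate.** Restore the protocol's no-oxygen condition, using recorded oxygen start and stop times. Keep the form item for chronic users, and state how it is coded when no oxygen form exists.

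If the sponsor prefers the present rules, the SAP should declare and justify the departure. The cost is SAP wording and programming. SpO2, pre-influenza SpO2 with its room-air flag, oxygen dates and the form item are already collected. What may be missing at some timepoints is a current reading on oxygen, hence the coding rule in item 2.

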2.2. Hypothesis

The outcome on the hospital recovery scale with pimodivir in combination with SOC treatment is statistically superior to treatment with placebo in combination with SOC treatment on Day 6 in hospitalized subjects with influenza A infection.

3. STUDY DESIGN AND RATIONALE

3.1. Overview of Study Design

This is a Phase 3 randomized, double-blind, placebo-controlled, multicenter study to evaluate the efficacy and safety of pimodivir in combination with SOC treatment vs placebo in combination with SOC treatment in adolescent (13 to 17 years), adult (18 to 65 years), and elderly (>65 to ≤85 years) hospitalized subjects with influenza A infection. A target of 600 hospitalized influenza-infected subjects will be randomly enrolled in this study with 300 subjects planned per treatment arm. The aim is to enroll a minimum of 60 adolescent subjects in this study in selected countries and study sites consistent with local regulations. The randomization will be stratified for baseline NEWS2 (4-5 or >5), type of baseline SOC (including or not including influenza antiviral treatment), and time since onset of influenza symptoms (first administration of study drug within 72 hours or between 72 and 96 hours since onset of influenza symptoms). The study population should consist of at least 75% of subjects (75% of the total planned sample size of 600 subjects) with first administration of study drug ≤72 hours since onset of influenza symptoms.

Subjects who meet all eligibility criteria will be randomized in a 1:1 ratio to receive 1 of the following treatments.

- Treatment Arm 1: pimodivir 600 mg bid for 5 days + SOC treatment*
- Treatment Arm 2: pimodivir placebo bid for 5 days + SOC treatment*

*SOC treatment is determined by the investigator based on local practice, and may include influenza antivirals and/or supportive care only. The choice to use influenza antivirals as part of the SOC should be made before randomization. The influenza antiviral should be started no later than the day of first study drug intake. An influenza antiviral as part of the SOC cannot be changed (eg, switching one influenza antiviral for another) during either the treatment period or extension phase, with the exception that an influenza antiviral may be discontinued in the case of a suspected AE.

Study drugs will be taken orally. During hospitalization, in case of medical need, study drug tablets may be dispersed in water before intake (in case of administration via a nasogastric tube or if the subject has difficulties swallowing the tablets). Refer to the pharmacy manual/study site investigational product manual for additional guidance on study drug preparation, handling, and storage.

Subjects (1) who complete the 5-day treatment, (2) who are still hospitalized upon treatment completion, (3) who are on invasive mechanical ventilation or who have an ongoing respiratory deficiency as evidenced by having a peripheral capillary oxygen saturation (SpO₂) <94% on room air, or in case of known pre-influenza SpO₂ <94% (eg, due to COPD), the current blood oxygen saturation on room air is lower than pre-influenza infection levels by at least 3%, (4) who, in the opinion of the investigator, are expected to derive clinical benefit from extending the treatment period, and (5) for whom the investigator agrees to extend treatment with the same SOC will be given the option for treatment extension. In the second blinded course of treatment, subjects will continue treatment with pimodivir or placebo for another 5 days in combination with continued SOC treatment. If the SOC contained no influenza antiviral during the first treatment period, no influenza antiviral can be started in the treatment extension as part of the SOC

[figure not shown]
The study will consist of a screening/baseline visit, a double-blind treatment period of 5 days (with the possibility to extend the treatment period), and a follow-up period of 23 days after the last dosing day. The entire study duration for each subject will be 28 days, except for subjects receiving extended treatment, for whom the study will last 33 days. The study is considered complete with the completion of the last study assessment for the last subject participating in the study.

The impact of influenza infection and its treatment on patient-reported symptoms will be evaluated throughout the study using a variety of tools. Sparse blood samples for the measurement of plasma concentrations of pimodivir will be taken on Days 1, 3 and 5 during hospitalization. In case subjects are discharged during the treatment period, a blood sample will be taken on the on-site or at-home visit on Day 6. The acceptability of the pimodivir formulation in adolescents will be assessed using a taste and swallowability questionnaire. Safety and tolerability will be assessed throughout the study from signing of the informed consent form (ICF)/assent form until the subject's last study-related activity. Safety evaluations will include the monitoring of AEs, clinical laboratory tests, 12-lead ECGs, vital signs, peripheral capillary oxygen saturation measurements, and (symptom-directed) physical examinations. Nasal mid-turbinate (MT) swabs for viral quantification and resistance testing will be collected.

A diagram of the study design is provided in [Figure 1](#).

Figure 1: Schematic Overview of the Study

63623872FLZ3001 – Overview

Abbreviations: bid: twice daily; MT: mid-turbinate; RT-PCR: reverse transcriptase polymerase chain reaction; SOC: standard-of-care.

*SOC treatment is determined by the investigator based on local practice, and may include influenza antivirals and/or supportive care only. The choice to use influenza antivirals as part of the SOC should be made before randomization. The influenza antiviral should be started no later than the day of first study drug intake. An influenza antiviral as part of the SOC cannot be changed (eg, switching one influenza antiviral for another) during either the treatment period or extension phase, with the exception that an influenza antiviral may be discontinued in the case of a suspected adverse event.

Subjects (1) who complete the 5-day treatment, (2) who are still hospitalized upon treatment completion, (3) who are on invasive mechanical ventilation or who have an ongoing respiratory deficiency as evidenced by having a peripheral capillary oxygen saturation (SpO₂) <94% on room air, or in case of known pre-influenza SpO₂ <94% (eg, due to COPD), the current blood oxygen saturation on room air is lower than pre-influenza infection levels by at least 3%, (4) who, in the opinion of the investigator, are expected to derive clinical benefit from extending the treatment period, and (5) for whom the investigator agrees to extend treatment with the same SOC will be given the option for treatment extension. In the second blinded course of treatment, subjects will continue treatment with pimodivir or placebo for another 5 days in combination with continued SOC treatment. If the SOC contained no influenza antiviral during the first treatment period, no influenza antiviral can be started in the treatment extension as part of the SOC.

An Independent Data Monitoring Committee (IDMC) will be commissioned for this study to monitor efficacy and safety data on a regular basis. Refer to Section 11.13, for details.

